## 11.4 Electrocardiogram (ECG)

At each timepoint, ECGs are collected in triplicate (any readings after the first three valid readings at a particular timepoint will be considered unscheduled). For numeric ECG variables, the mean of the valid values at each timepoint will be taken. For qualitative ECG results, the worst case will be used. Baseline for numeric ECG results is the mean of the available valid values at the last timepoint with any non-missing data prior to the first dose of investigational product in that period. For qualitative ECG results, baseline will be the worst case at the last timepoint with any non-missing data prior to the first dose of investigational product in that period.

Descriptive statistics for ECG variables (eg, heart rate, PR interval, QRS interval, QT interval, and QTc interval) and their changes from baseline at each assessment time point will be presented by treatment. QTc interval will be calculated using both Bazett ( $QTcB=QT/(RR)^{1/2}$ ) and Fridericia ( $QTcF=QT/(RR)^{1/3}$ ) corrections; and if RR is not available, it will be replaced with 60/hr in the correction formula. ECG interpretation will be summarized by visit. A shift table from baseline to each timepoint for qualitative ECG results will be presented. All ECG results will be listed for each subject in the Safety Analysis Set.

Electrocardiogram variable values will be considered PCI if they meet or exceed the upper limit values listed in [Table 7](#). Assessment of whether a value is PCI will be based on the derived average at each timepoint for each subject. The number and percentage of subjects with post-baseline PCI values will be tabulated by treatment. The percentages will be calculated relative to the number of subjects with available non-PCI baseline and at least 1 post-baseline assessment. The numerator is the total number of subjects with at least 1 PCI post-baseline ECG value. A listing of all subjects with post-baseline PCI value will be provided including the subject number, site, baseline, and post-baseline PCI values.

Table 7: Criteria for Potentially Clinically Important ECG Values	
Parameter	Upper Limit
QTcB	> 500 ms, > 480 ms, >450 ms
QTcF	> 500 ms, > 480 ms, >450 ms
QTcB	An increase from Baseline of $\geq 60$ ms and $\geq 30$ ms
QTcF	An increase from Baseline of $\geq 60$ ms and $\geq 30$ ms

## **11.5 Other Safety Variables**

Anti-PTH antibodies will be assessed at Treatment Period 1 Day 1 (pre-dose) and at Follow-up. The results at each timepoint will be summarized for all subjects overall.

## 12. CLINICAL PHARMACOKINETIC AND PHARMACODYNAMIC ANALYSES

### 12.1 Pharmacokinetics Population and Pharmacodynamic Population

The Pharmacokinetic Set consists of subjects who do not have major protocol violations that affect the validity of the PK results, receive at least 1 dose of rhPTH(1-84) and have at least 1 evaluable post-dose pharmacokinetic concentration value available for 1 dose regimen. See details in Section 4.4. A listing of subjects excluded from the PK set along with the reasons for exclusion will be generated.

The Pharmacodynamic Analysis Set consists of subjects who do not have major protocol violations that affect the validity of the PD results, receive at least 1 dose of rhPTH(1-84) and have at least 1 evaluable post-dose pharmacodynamic value available for 1 dose regimen. See details in Section 4.4. A listing of subjects excluded from the PD set along with the reasons for exclusion will be generated.

### 12.2 Handling BLQ and Missing Values

The following procedures will be used for raw plasma PTH concentrations, raw serum pharmacodynamic data, and raw urine pharmacodynamic data below the lower limit of quantification (LLOQ):

- Plasma samples that are BLQ are reported as <LLOQ on the data listings, where LLOQ is replaced by the actual value for LLOQ.
- Missing values may be imputed on a case-by-case basis

For plasma PTH concentrations the following guidance will be followed:

- Samples that are BLQ are treated as zero in the calculation of summary statistics (e.g. mean, SD, etc.) for the plasma concentrations at individual time points.
- Mean concentrations are reported as zero if all values are BLQ, and no descriptive statistics are reported. If the calculated mean ( $\pm$  SD) concentration is less than the LLOQ, the value will be reported as calculated. The mean values derived using these conventions will be used to create the mean plasma concentration versus time plots.
- For calculation of area under the plasma concentration curve (AUC), BLQ values are set equal to zero in the dataset loaded into WinNonlin for pharmacokinetic analysis. WinNonlin uses the zero values that occur before the first time point with a concentration greater than LLOQ. Values that are BQL after the first measurable concentration are set to “missing” in the dataset loaded into WinNonlin

For serum PD concentrations the following guidance will be followed:

- Samples that are BLQ are treated as half the LLOQ in non-compartmental PD analysis and the calculation of summary statistics (e.g. mean, SD, etc.) for the plasma concentrations at individual time points.

### **12.3 Pharmacokinetic Methods**

All summaries and analyses of the pharmacokinetic data will be based on the Pharmacokinetic Set. After database lock, a visual inspection of concentration-time profiles and pharmacokinetic parameters will be performed by PRA to determine dataset integrity and potential outliers. Descriptive statistics of pharmacokinetic parameters may be calculated with and without subjects with potential outlier data. Subjects with potential outlier data will be reviewed by Shire for inclusion/exclusion from the descriptive statistics on a case-by-case basis.

#### **12.3.1 Raw PTH Concentration Data**

For subjects and treatment periods when one dose is received, samples for pharmacokinetic analysis are taken at Predose, 10, 20 and 30 minutes, 1, 1.5, 2, 4, 8, 12, 16 and 24 hours. For subjects and treatment periods when two doses are received, samples for pharmacokinetic analysis are taken at Predose, 10, 20 and 30 minutes, 1, 1.5, 2, 4, and 8 hours. A second predose sample will be collected just before the second dose is administered 12 hours after the first dose, 10, 20 and 30 minutes following the second dose, and 13, 13.5, 14, 16, 20, 24, 28 and 36 hours after the first dose. Plasma concentrations of PTH(1-84) will be measured using a validated analytical method.

#### **12.3.2 Baseline-adjusted PTH Concentration Data**

Baseline-adjusted PTH concentrations (subject- and period-specific) are to be calculated by subtracting baseline endogenous PTH from the raw PTH concentrations. The baseline is defined as pre-morning-dose endogenous PTH level on Day 1 for each treatment period. Since rhPTH(1-84) is administered to subjects with hypoparathyroidism in this study, baseline endogenous PTH levels are expected to be low and likely below the lower limit of quantification (LLOQ) for PTH. If the baseline-adjusted PTH concentration gives a negative value then the baseline-adjusted PTH concentration should be set to zero. In the terminal phase (after the morning dose during the QD treatment and after the evening dose during the BID treatment), any positive baseline-adjusted PTH concentrations following a negative value will be assigned a value of zero.

If the pre-dose PTH value is missing, then this is set to 0 for the calculation of the baseline-adjusted PTH concentration for the purposes of calculating the baseline-adjusted pharmacokinetic parameters.

#### **12.3.3 Pharmacokinetic Parameters**

The pharmacokinetic analysis will be conducted by using WinNonlin Phoenix version 6.3 or higher (Pharsight Corporation, Mountain View, California, USA). Pharmacokinetic

parameters will be determined from the plasma PTH concentration-time data by non-compartmental analysis. Pharmacokinetic analyses based on raw and baseline adjusted PTH concentrations will be performed. In each treatment period, all assessment dates will be related to the first day of rhPTH administration. This first day of investigational product administration is referred to as Day 1. Day-1 is the day that is preceding Day 1, and a Day 0 will not be defined.

The pharmacokinetic parameters will include, but may not be limited to:

- Time of maximum observed concentration sampled during a dosing interval ( $t_{max}$ ), to be reported in the unit of hour (original and baseline-adjusted)
- Maximum observed concentration ( $C_{max}$ ), to be reported in the unit of pg/mL (original and baseline-adjusted)
- Area under the curve from the time of dosing to the last measurable concentration ( $AUC_{last}$ ). Calculated using the linear up/log down method, to be reported in the unit of pg.hr/mL (original and baseline-adjusted)
- Area under the curve extrapolated to infinity calculated as  $AUC_{last} + C_{last}/\lambda_z$  ( $AUC_{0-inf}$ ). Calculated using the linear up/log down method, to be reported in the unit of pg.hr/mL (baseline-adjusted only)
- % of AUC extrapolated from the last measurable concentration to infinity over  $AUC_{(0-inf)}$  (%AUC extrapolated) (baseline-adjusted only)
- Area under the concentration curve from time zero to 24 hours post the first dose ( $AUC_{0-24h}$ ), to be reported in the unit of pg.hr/mL (calculated using the linear up/log down method) (original and baseline-adjusted)
- Area under the concentration curve from time zero to 12 hours post the first dose ( $AUC_{0-12h}$ ) calculated using the linear up/log down method, to be reported in the unit of pg.hr/mL (for BID treatment only, original and baseline-adjusted)
- Area under the concentration curve from the time of the second dose to 12 hours post the second dose ( $AUC_{12-24h}$ ) calculated using the linear up/log down method, to be reported in the unit of pg.hr/mL (for BID treatment only, original and baseline-adjusted)
- Elimination rate constant associated with the terminal (log-linear) portion of the curve ( $\lambda_z$ ) (baseline-adjusted only)
- Terminal half-life ( $t_{1/2}$ ), calculated as  $0.693/\lambda_z$  (baseline-adjusted only)
- CL/F Apparent total body clearance, calculated as  $Dose/AUC_{0-inf}$  (baseline-adjusted only)
- $V_{ss}/F$  Apparent volume of distribution at steady state, calculated as  $MRT \times CL/F$ , where MRT is mean residence time calculated as  $AUMC_{0-inf}/AUC_{0-inf}$  and  $AUMC_{0-inf}$  is the area under the first moment curve extrapolated to infinity. (baseline-adjusted only)

All pharmacokinetic parameter calculations will be performed using actual times calculated relative to the start of the study drug administration on Day 1 for each period. The pharmacokinetic parameters  $\lambda_z$ ,  $t_{1/2}$ ,  $AUC_{0-inf}$ ,  $CL/F$ , and  $V_{ss}/F$  will not be calculated for patients with PTH concentration-time profiles (baseline-adjusted) that do not exhibit a terminal log-linear phase.

If a pre-dose sample is missing, or if a 12 hour sample in the BID treatment is missing, then for the purposes of calculating the pharmacokinetic parameters, these values will be set to 0.

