SERMs	selective estrogen receptor modulators
$t_{1/2}$	time to elimination of half of the drug
$T_{max}$	time to maximum concentration
$TE_{max}$	time to maximum effect
UK	United Kingdom
US	United States
$V_z/F$	volume of distribution during terminal phase

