## 9.8 Pharmacokinetic and Pharmacodynamic Analyses

### 9.8.1 Pharmacokinetic Analysis

All pharmacokinetic analyses will be performed using the pharmacokinetic population.

Pharmacokinetic parameters will be determined from the plasma concentration-time data for PTH and by non-compartmental analysis. Pharmacokinetic analyses based on raw and baseline-adjusted PTH concentrations will be performed. The baseline is defined as the predose endogenous PTH level on Day 1, and baseline-adjusted PTH concentrations are to be calculated by subtracting baseline PTH from the raw PTH concentrations. All assessment dates will be related to the first day of rhPTH(1-84) administration.

This first day of investigational product administration is referred to as Day 1. Day 1 is the day that is preceding Day 1, and a Day 0 will not be defined.

The pharmacokinetic parameters will include, but not be limited to:

- maximum observed concentration maximum ( $C_{\max}$ )
- time of maximum concentration ( $T_{\max}$ )
- area under the concentration curve (from time zero to the last measurable concentration and from time zero to infinity ( $AUC_{0-t}$  and  $AUC_{0-\infty}$ ))
- area under the concentration curve from time zero to 24 hours post the first dose ( $AUC_{0-24h}$ )
- elimination rate constant ( $K_{el}$ )
- apparent clearance ( $CL/F$ )
- apparent volume of distribution ( $V_z/F$ )
- elimination half-life ( $t_{1/2}$ )

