## **17. CHANGES TO ANALYSES SPECIFIED IN PROTOCOL**

There were no changes to the analysis planned in the latest version of the protocol.

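### SAP 12.3.3 replaces the protocol's Vz/F, without declaring it, by a Vss/F that includes absorption time and so overstates volume in every once-daily period

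*SAP*

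**What the plan says.** **Protocol.** The synopsis (Pharmacokinetic Endpoints) and Section 9.8.1 both list an "apparent volume of distribution" with the symbol Vz/F. The abbreviations list explains the symbol as "volume of distribution during terminal phase". No formula is given, and the parameter is not restricted to one regimen. Section 9.8.1.1 says that the PK parameters will be both listed and summarised by treatment.

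**SAP.** Section 12.3.3 has no Vz/F. Its volume parameter is Vss/F, "Apparent volume of distribution at steady state", calculated as MRT × CL/F, "where MRT is mean residence time calculated as" AUMC0-inf/AUC0-inf, for baseline-adjusted data only. The same list has "CL/F Apparent total body clearance, calculated as" Dose/AUC0-inf, and does not say whether Dose in a twice-daily period is one injection or the day's total. On timing: "All pharmacokinetic parameter calculations will be performed using actual times calculated relative to the start of the study drug administration on Day 1". Section 12.3.4 lists CL/F and Vss/F by subject but keeps them out of the summary tables. Section 17 states: "There were no changes to the analysis planned in the latest version of the protocol".

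**The concern.** There are two faults. First, a parameter that the protocol names is missing from the SAP, another stands in its place, and the section meant to record such changes says there are none. Second, the replacement does not measure what its label says. MRT × CL/F gives a steady-state volume when MRT is the residence time of drug already in the body, as after an intravenous bolus. Here every dose is subcutaneous, so AUMC/AUC also counts the time spent at the injection site, and the SAP makes no correction for it.

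If nothing changes, the study report will omit a protocol parameter, list a volume that mixes in absorption rate, and state that the analysis followed the protocol. The absorption part is separate from the 12-hour offset between doses in twice-daily periods. It is present in every once-daily profile, and re-timing the twice-daily profiles would not remove it.

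**Working it through.** The documents give no half-life, absorption rate or volume, so there is no figure of the plan's own to reproduce. The direction follows from the SAP's formula; the size needs assumed rates.

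**Inputs from the documents.** MRT = AUMC0-inf/AUC0-inf, CL/F = Dose/AUC0-inf and time zero at the first dose (SAP 12.3.3). One subcutaneous dose in once-daily periods, and two equal doses 12 h apart in twice-daily periods (Protocol 3.1).

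**Assumed, not in the documents.** Linear kinetics throughout. For size only: one compartment with first-order absorption (ka) and elimination (ke), elimination half-life 0.5 to 3 h, and absorption half-life 0.25 to 3 h (25 combinations).

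**Once-daily periods.**
- After an extravascular dose, AUMC/AUC = MRT(disposition) + MAT.
- Hence MRT × CL/F as the SAP defines it = Vss/F + MAT × CL/F. MAT is positive, so the value is too high whatever the rates.
- With one compartment, AUMC/AUC = 1/ke + 1/ka and CL/F = ke × V/F, so the ratio to the true V/F is 1 + ke/ka. The term ke/ka is the absorption half-life divided by the elimination half-life.
- Half-life ratios of 0.25, 0.5 and 1 give 1.25, 1.5 and 2.0.
- Over the 25 combinations the ratio runs from 1.08 (elimination 3 h, absorption 0.25 h) to 7.0 (elimination 0.5 h, absorption 3 h). With linear-up/log-down areas on the SAP's once-daily sampling times it runs from 1.09 to 7.10, so the sampling schedule adds little.

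**Twice-daily periods.**
- For two equal doses at 0 and 12 h, timed from the first, MRT rises by (0 + 12)/2 = 6 h.
- If Dose is the daily total, the ratio is ke × (1/ke + 1/ka + 6).
- If Dose is one injection against the AUC of both, CL/F and the ratio are halved. The value is then too high only when MAT + 6 h exceeds MRT(disposition).

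Worked case with elimination half-life 1 h and absorption half-life 0.5 h, so 1/ke = 1.443 h and 1/ka = 0.721 h:

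| Period | Calculation | Ratio to true V/F |
|---|---|---|
| Once daily | 0.693 × (1.443 + 0.721) | 1.50 |
| Twice daily, total dose | 0.693 × (1.443 + 0.721 + 6) | 5.66 |
| Twice daily, one injection | 5.66 / 2 | 2.83 |

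Over the 25 combinations the twice-daily ratio is 2.47 to 15.3 with the total dose and 1.23 to 7.66 with one injection.

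**The protocol's parameter on the same basis.** Vz/F = (CL/F)/λz in once-daily periods equals the true V/F (ratio 1.00) when absorption is at least as fast as elimination. When absorption is slower, λz reflects ka and Vz/F is too high as well, at 1.33 to 6.0 times V/F in the assumed range. MRT × CL/F exceeds it in all 25 cases: by V/F × ke/ka when absorption is at least as fast, and by V/F when it is slower.

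**The case against.** The strongest reply is that this is a small documentation discrepancy. Both parameter lists are open-ended, so adding Vss/F is allowed. CL/F and λz are both derived, so Vz/F is one division away for any subject who has them, and no information is lost. The volume appears only in listings, the study is descriptive without hypothesis tests, and no stated comparison or decision uses it. All of that stands and keeps the point minor. It does not answer the omission of a named parameter, because an open-ended list permits additions rather than silent removal. Nor does it correct the label on the value that will be listed.

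It is also fair to say that Vz/F is no clean substitute. It is biased upward when absorption is rate-limiting, and in a multi-compartment model it is a different quantity from Vss/F. Restoring it meets the protocol and removes the residence-time error, but does not guarantee an unbiased volume.

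A reader might infer that the inflated volume would carry into the population PK model. The documents do not support that: Protocol 9.8.4 builds the model by fitting PK and PD data, SAP 12.6 leaves it to a separate plan, and neither says that non-compartmental volumes enter it.

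**Conclusion.** The point holds as a minor one. SAP 12.3.3 substitutes Vss/F for the protocol's Vz/F, and the statement in SAP 17 is not correct for this parameter. In once-daily periods the listed Vss/F is too high by MAT × CL/F. That direction rests only on subcutaneous dosing and linear kinetics.

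The size is not established. The factors of 1.25 to 2.0 hold for one compartment with absorption no slower than elimination, at assumed half-life ratios of 0.25 to 1; slower absorption gives more.

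It would be tempting to say that volume is overstated in twice-daily periods with the same certainty. The extra 6 h of MRT is certain for equal doses, but the net sign depends on the undefined Dose. It is upward throughout the assumed range under either reading, and with a single-injection Dose that is not guaranteed in general. No summary table and no result for the primary objective changes.

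**What to change.** - **SAP 12.3.3:** add Vz/F = (CL/F)/λz from the baseline-adjusted profile, as the parameter that the protocol names. The formula has to be written in the SAP, since the protocol gives only the name and symbol.
- **Twice-daily periods:** state which Dose and which AUC enter CL/F and Vz/F. Alternatively, give Vz/F for once-daily periods only and declare that in SAP 17, because the protocol sets no such limit.
- **MRT × CL/F:** drop it, or keep it under a label that says it includes absorption time.
- **Consequential edits:** change the Vss/F mentions in the rule on profiles without a terminal log-linear phase (end of 12.3.3) and in the listing rule in 12.3.4, and the content of Listing 5.4.
- **SAP 17:** record every departure that is kept, including listing CL/F and volume without summarising them, which differs from Protocol 9.8.1.1.
- **Interpretation:** note beside the listing that Vz/F is also too high if absorption is slower than elimination.

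The cost is a handful of text edits and one derived column. λz and AUC0-inf are already calculated, and no new data are needed.

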### **12.3.4 Statistical Analysis of Pharmacokinetic Data**

Individual PTH concentrations (raw and baseline-adjusted) will be listed and summarized with descriptive statistics (number, arithmetic mean, SD, coefficient of variation [CV%], median, minimum, and maximum) by treatment and day. Pharmacokinetic parameters of PTH (based on raw and baseline-adjusted PTH concentrations) will be listed and summarized with descriptive statistics (number, arithmetic mean, SD, coefficient of variation [CV%], median, minimum, maximum, geometric mean, and geometric CV%) by treatment.  $CL/F$  and  $V_{ss}/F$  will be listed, but not included in summary tables.

For Treatment B (repeated in Cohort 1 and Cohort 2) and Treatment E (repeated in Cohort 3 and Cohort 4), summary statistics (for both concentration data and pharmacokinetic parameters) will be prepared by cohort as well as for overall (combining different cohorts).

Figures of individual (overlaid by treatment) and mean (+/-SD) concentration-time profiles (overlaid by treatment as well as by rhPTH(1-84) dosing regimen) of raw and baseline-adjusted plasma PTH will be generated on linear and semi-log scales.

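### The SAP's twice-daily (BID) rules stop short of three items: listed BID Vss/F is wrong as written, tabulated BID Cmax and tmax name no dosing interval, and tabulated serum extremes have no hour window

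*SAP*

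**What the plan says.** SAP 12.3 and 12.4 adapt several items to BID dosing. The terminal phase is taken "after the evening dose during the BID treatment" (12.3.2). A partial AUC covers 0-12 h, and another is the "Area under the concentration curve from the time of the second dose to 12 hours post the second dose" (12.3.3). Urine has two extra BID intervals, out to 36 h (12.4.4).

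The other definitions in 12.3.3 make no such distinction:
- The clock: "All pharmacokinetic parameter calculations will be performed using actual times calculated relative to the start of the study drug administration on Day 1", which for BID means the morning dose.
- Vss/F is MRT times CL/F, "where MRT is mean residence time calculated as" AUMC0-inf divided by AUC0-inf.
- CL/F is "Apparent total body clearance, calculated as" Dose over AUC0-inf. Dose is not defined for two injections.
- tmax is the "Time of maximum observed concentration sampled during a dosing interval". Cmax names no interval.

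Under 12.3.4, CL/F and Vss/F "will be listed, but not included in summary tables". Cmax and tmax are summarised by treatment.

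For serum markers, 12.4.3 limits the AUCs to 0-24 h. It gives Emax, Emin, TEmax and TEmin no hours and says only that parameters are estimated for Day -1 and Day 1. Section 12.4.5 summarises the same parameters for Day -1 and Day 1/2.

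**The concern.** The MRT formula is a single-dose formula. Applied to two injections on a clock that starts at the first, it counts the wait for the second injection as residence time, and that error passes straight into BID Vss/F.

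The other two items are ambiguous rather than wrong. Two competent programmers could produce different BID values of tmax, Cmax, Emax, Emin, TEmax and TEmin from the same data, each consistent with the text. The study tests no hypothesis and its rationale sets BID against QD, so readers will compare these rows directly. Part of a tabulated BID-QD difference could then come from the definition and not from the regimen.

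**Working it through.** The plan states no MRT, Vss/F or tmax figure to reproduce.

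**1. MRT and Vss/F.** Inputs: two equal doses 12 h apart (SAP 2.1) and time counted from the first dose (12.3.3). Assumptions: linear kinetics, and the same mean residence time M after each dose. Let A1 and A2 be the AUCs due to each dose and s = A2/(A1 + A2).
- AUC0-inf = A1 + A2
- AUMC0-inf = A1 × M + A2 × (M + 12)
- MRT as written = M + 12s

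The gain is 12 × 0.5 = 6.0 h for equal shares, 12 × 0.4 = 4.8 h and 12 × 0.6 = 7.2 h. With the total dose in CL/F, Vss/F is multiplied by (M + 12s)/M. The documents give no half-life, so M is assumed:

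| M (h) | Factor at s = 0.5 |
|---|---|
| 2 | 8/2 = 4.0 |
| 3 | 9/3 = 3.0 |
| 5 | 11/5 = 2.2 |
| 8 | 14/8 = 1.75 |

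At M = 3 h the factor is 7.8/3 = 2.6 for s = 0.4 and 10.2/3 = 3.4 for s = 0.6.

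Numerical check: non-compartmental analysis (linear up/log down) on the SAP's 12 QD and 21 BID sampling times, using an assumed one-compartment model with absorption rate 3/h and half-life 1 to 4 h. The gain was 6.00 h at every half-life; at 2 h, MRT was 3.24 h for QD and 9.24 h for BID.

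**2. tmax.** Take 8 subjects, of whom k peak after the second dose (k is assumed; no document gives it). If all peak at the same time after their dose, mean tmax on the SAP clock is later by 12k/8 = 1.5k h, and the SD is 12 × √(k(8 − k)/56): 4.24 h at k = 1 and 6.41 h at k = 4. Letting each peak fall at any scheduled time from 10 min to 2 h after a dose gives these SD ranges:

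| k | SD of tmax (h) |
|---|---|
| 0 or 8 | 0 to 0.98 |
| 1 or 7 | 3.59 to 4.89 |
| 4 | 5.43 to 7.39 |

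The median averages the 4th and 5th ordered values. Both lie in the same cluster unless k = 4.

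**3. Serum extremes.** From the detailed schedules in SAP 2.4:
- QD, 11 times: predose, 1.5, 4, 6, 8, 10, 12, 13.5, 16, 20 and 24 h.
- BID, 15 times: the same plus 18, 22, 28 and 36 h.

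Relative to the second dose, BID is sampled at 1.5, 4, 6, 8, 10, 12, 16 and 24 h. A 0-24 h window keeps 6 of these 8, the last at 12 h. Protocol 2.1 puts the maximum mean calcium rise 12 h after a dose, with no return to baseline by 24 h. For the second dose that is 12 + 12 = 24 h, the edge of such a window.

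The day labels do not settle the matter. A literal Day 1 limit would lose the 24 h sample, which falls on Day 2 and which the 0-24 h AUC needs. Day 1/2 would admit 28 and 36 h for BID only. The protocol's rationale gives 24-36 hours in the Synopsis and 24 hours in Section 2.1.

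**The case against.** The strongest reply is that little of this touches the main comparison. MRT is only an intermediate, and Vss/F appears only in listings. Matched BID-QD outputs are already planned: serum AUCs over 0-24 h, 24 h urinary excretion, and concentrations by time point with overlaid plots. The tmax wording admits a per-interval reading, parallel to the BID partial AUCs. TEmax and TEmin would themselves show an extreme after 24 h. Table specifications sit in a separate document not seen here (SAP 1) and might fill the gaps.

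Most of this stands as a limit on impact. It does not make the tabulated tmax and serum extremes comparable between regimens, and SAP 1 assigns the technical detail of the PK and PD analyses to the SAP itself.

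A reader might go further than the text allows:
- That CL/F for BID is wrong. AUC0-inf spans both injections, so only the total dose gives a clearance. Entering one injection would halve CL/F, but nothing says that will be done. The undefined Dose is a documentation gap.
- That the median tmax is uninterpretable whenever peaks mix. With 8 subjects it falls between the clusters only at a 4:4 split.
- That replacing Vz/F (Protocol 9.8.1) with Vss/F is a BID error. It affects both regimens and is a documentation point, since SAP 17 records no change.
- That subtracting 6 h repairs MRT. That holds only for equal AUCs. At a 40-60% share it leaves 1.2 h of error either way, which is 1.2/3 = 40% of Vss/F at M = 3 h.

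**Conclusion.** The point holds for three items of unequal weight. BID Vss/F is wrong as written, with the factors above depending on linear kinetics, the assumed MRT and the second dose's AUC share; the damage is confined to listings. BID tmax and Cmax are under-specified in tabulated output, and a mean and SD of tmax can be dominated by which dose each subject peaked after; whether that happens depends on an unknown k. The serum extremes are under-specified in tabulated output and can cover 36 h for one regimen and 24 h for the other; the effect on Emax and Emin cannot be derived from the documents.

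A reader might infer that the BID-QD comparison as a whole is compromised. The documents do not support that, because the planned matched summaries are unaffected. These definitions should be settled before database lock, but they do not threaten the study's validity.

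**What to change.** 1. Preferably, do not report BID Vss/F. Otherwise subtract from BID MRT the actual interval between doses times the second dose's AUC share; half the interval is valid only if the two AUCs are equal. State that Dose in CL/F is the period total, and record the Vz/F to Vss/F change in SAP 17.
2. Report BID Cmax and tmax separately for 0-12 h and 12-24 h, with the second tmax timed from the second dose. Keep the overall Cmax.
3. State the window for Emax, Emin, TEmax and TEmin, and align the day labels in 12.4.3 and 12.4.5. Tabulate a matched 0-24 h value for the BID-QD comparison, with the BID 0-36 h value beside it.

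The cost is SAP wording, a change to the non-compartmental set-up and a few extra table rows; no new data are needed. Neither window in item 3 is ideal: 0-24 h ends 12 h after the second dose and may miss its peak, and 0-36 h observes BID for longer than QD. That is why both should be shown.
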